2.8. Methods

2.8.1. Drugs and Dosage

Upon enrollment in the study, the participant will be randomly assigned to the Low Dose or the Fully Active Dose condition. Condition assignment will be performed with a table of random numbers generated by the Institute for Statistics, University of Bern. All study investigators will remain blind to condition assignment. If there is an adverse event or other emergency requiring knowledge of participant's condition assignment, the blind may be broken for an individual participant.

Participants in the Low Dose condition are assigned to receive an initial dose of 25 mg MDMA followed 2.5 hours later by a supplemental dose of 12.5 mg MDMA. Participants assigned to the Fully Active dose condition will receive an initial dose of 125 mg followed 2.5 hours later by a supplemental dose of 62.5 mg MDMA. Eight of 12 subjects, or 66.6%, will be assigned to the Fully Active dose condition, and 4 of 12, or 33.3%, will be assigned to the Low Dose condition.

The two doses of MDMA chosen for the Low Dose condition have been selected on the basis of their ability to produce minimal but detectable subjective effects (Grob et al. unpublished; Harris et al. 2002) and thus serve as an active placebo. The cumulative dose of 37.5 mg MDMA is not expected to produce a significant reduction in anxiety or a significant increase in access to emotionally upsetting material, though this dose may produce slight alterations in consciousness, such as increased relaxation or tension (Harris et al. 2002). The initial 125 mg dose of MDMA selected for the Fully Active Dose condition was chosen on the basis of case reports of MDMA-assisted psychotherapy conducted in the US prior to scheduling (Greer and Tolbert 1986), as well as on data obtained from [name] MAPS-sponsored MDMA/PTSD pilot study currently underway in the United States. This dose is expected to reduce fear in response to emotionally upsetting thoughts, feelings or memories and to increase access to emotionally intense material, and is thus expected to be therapeutically active. Doses equal to or exceeding 125 mg have been employed in previous uncontrolled and controlled studies of MDMA (Cami et al. 2000; Grob et al. 1996; Grob et al. Unpublished; Harris et al. 2002; Lester et al. 2000; Mas et al. 1999; Styk 2007; Tancer et al. 2001; Tancer et al. 2003; Vollenweider et al. 1998).

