With participants carefully monitored for any indicators of adverse events, the initial doses of either 125 mg or 150 mg, and the cumulative dose of 187.5 mg or 225 mg respectively will prove to be tolerable and pose no more than minimal risk. The side effect profile is expected to increase with the higher dose but it is considered unlikely that there will be any Serious Adverse Events (SAEs) or any persisting side effects.

Table 1. Dose Regimen

	Initial Dose	Supplemental Dose	Cumulative Dose
Low Dose	25 mg	12.5 mg	37.5 mg
Fully Active Dose	125 mg	62.5 mg	187.5 mg
20% Larger Active Dose	150 mg	75 mg	225 mg

Supplemental doses for both the Low and the Fully Active dose conditions were chosen to be half the size of initial doses, and the dosage and schedule of dosing was chosen on the basis of case reports describing the use of MDMA in psychotherapy (Greer and Tolbert 1998; Stolaroff 2004, Styk 2007). Supplemental dosing performed 2.5 hours after the initial dose is expected to extend the course of drug effects without increasing their intensity. Both the Low and Fully Active dose conditions use supplemental doses that are half of the initial dose, to make dosing schedule equivalent across the conditions.

Participants will receive an initial dose of MDMA approximately 1 to 1.5 hours after they arrive at [name] office for each experimental session. If the investigators believe the participant is able to tolerate a supplemental dose and the participant agrees to take it, then a supplemental dose will be offered 2.5 hours later. The investigators will not administer the supplemental dose if the participant is exhibiting signs or symptoms that would place him or her at greater risk of experiencing a serious adverse event.

Each dose will consist of the specified amount of racemic MDMA mixed with an inactive substance, such as lactose, to prevent the investigators from distinguishing doses through weight or appearance of the capsules. Initial doses will be distinguished from supplemental doses through labeling them "Dose 1" and "Dose 2" or "first" and "second" dose to ensure that the correct dose is administered at the scheduled time. Each dose of MDMA will be administered along with 250 to 300 mL electrolyte-containing fluid. MDMA will be administered during each of the three experimental sessions, with the second and third session scheduled to fall two to four weeks after the previous experimental session.

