2.8.2. Assessments and Measures

Psychiatric diagnoses will be made through the Structured Clinical Interview for Diagnoses (SCID), and PTSD symptoms will be measured by the Clinician Administered PTSD Scale (CAPS) during screening to determine whether an individual may participate in the study.

PTSD symptoms will be assessed six times in this study:

- T0: *Baseline assessment*
- T1: *Post MDMA 2 assessment*: 3 weeks after the second experimental session (MDMA 2)
- T2: *End of treatment assessment*: 3 weeks after the third experimental session (MDMA 3)
- T3: *1st follow-up assessment*: 2 months after the third experimental session (MDMA 3)

T4: *2nd follow-up assessment*: 6 months after the third experimental session (MDMA 3) for all participants assigned to the Fully Active Dose condition, and all participants assigned to the Low Dose condition who choose not to take part in the open-label study continuation.

T5: *3rd follow-up assessment*: 12 months after the third experimental session (MDMA 3) for all participants assigned to the Fully Active Dose condition, and all participants assigned to the Low Dose condition who choose not to take part in the open-label study continuation.

Participants who choose to take part in the open label study continuation “Stage 2” will be assessed identically to stage 1 three weeks after the second and third (end of treatment) experimental sessions and two, six and twelve months after the third experimental session in Stage 2. The T2 assessment will serve as baseline for stage 2.

Participants who choose to take part in the open label study continuation “Stage 3” will be assessed identically to stage 1 three weeks after the second (end of treatment) experimental session and two, six and twelve months after the experimental session in Stage 2. The T3 assessment will serve as baseline for stage 3.

All outcome measures will be administered by an independent assessor. The independent assessor will remain blind to subject condition and will not be present during psychotherapy sessions. The CAPS will serve as the primary outcome measure, and the PDS will serve as additional measure of PTSD symptoms. The CAPS and the PDS are specifically designed to assess PTSD. German versions of all measures will be used in this study.

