2.8.4. Methods and Schedule of Events

Table 2: Schedule of events:

Time																	
	h=hour																
	d=day																
	w=week																
	m=month																
weeks from start	-4 to -2	0	1	2	3	3 + 1 d	4	5	6	6 + 1 d	7	8	9	9	9 + 1 d	10	11
Medical Exam	x															x	
Informed consent	x																
SCID	x																
Metabol. profile, Thyroid Panel	x															x	
Liver Enzymes	x															x	
ECG	x																
Urine Drug Screen ³	x					x				x				x		x	x
Urine Pregancy Screen	x					x				x				x			
EEG/ Startle	x															x	
SCID	x														x	x	x
CAPS		x										x			x	x	x
PDS		x				x				x			x		x	x	x
RRPQ																	x
Nondrug Therapy			x	x		x	x	x		x	x	x		x	x	x	x ²
MDMA Therapy					x				x				x				
Vital Signs	x				x				x				x				
SUDS					x				x			x		x			
Both			x ¹	x ¹	x	x			x	x			x	x			

therapists present																
--------------------	--	--	--	--	--	--	--	--	--	--	--	--	--	--	--	--

x¹: Both therapists present at either one of the two introductory sessions.

x²: A half-hour closing meeting with the investigators; Participants learn condition assignment.

³: Urine drug testing will be done once additionally at random during the treatment phase

The study consists of eleven non-drug psychotherapy sessions, three sessions of MDMA-assisted psychotherapy, and five separate administrations of outcome measures (see Table 2). Most non-drug psychotherapy sessions will be scheduled on a weekly basis, and the three experimental sessions will be scheduled three to five weeks apart. The open-label continuation of the study (“Stage 2”) will be nearly identical in structure to the active-placebo controlled study except that only one introductory session is scheduled prior to the first experimental session. MDMA-assisted therapy will be performed by [name] and [name], a female co-therapist. Both therapists will also be present during one of the introductory therapy sessions and during each of the three psychotherapy sessions scheduled to occur 24 hours after each MDMA-assisted psychotherapy session. After psychiatric and medical screening, a total of 14 visits will occur according to Table 2.

2.8.5. *Nature of MDMA-assisted Psychotherapy*

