2.8.6. Open Label Continuation for Active Placebo Patients ("Stage 2")

After each participant completes all outcome measures on the session scheduled 3 weeks after the third experimental session (T2), the participant will have a 30-minute meeting with the principal investigator. During this meeting, the blind will be broken for the individual participant while retaining the blind for the independent assessor. If a participant had received the Low (25 mg followed 2.5 hours later by 12.5 mg) dose of MDMA during the course of the study, she or he would be offered an opportunity to enroll in the open label continuation of the study, referred to as Stage 2. He or she would give written informed consent to take part in this second stage of the study, with consent given separately from the initial consent. If the participant consents to take part in Stage 2 of the study, he or she would receive the Fully Active dose of MDMA (125 mg followed 2.5 hours later by 62.5 mg) during three experimental sessions scheduled two to four weeks apart. Outcome measures administered three weeks after the third experimental session will serve as baseline measures for Stage 2. The participant would undergo one preparatory non-drug psychotherapy session 1 to 2 weeks prior to the first experimental session, and he or she would receive non-drug psychotherapy follow-up sessions according to the same schedule described for the active placebo controlled study. Procedures for non-drug psychotherapy sessions, experimental sessions, weekly telephone contact and outcome measure administration will be the same as those employed in the first stage of the study.

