5.2 Safety Measures

- Subjective Units of Distress (SUD)
- Vital signs (Systolic blood pressure (SBP), diastolic blood pressure (DBP), heart rate (HR), body temperature (BT))
- Spontaneously reported reactions during experimental sessions and seven days afterward
- Adverse events reported during the study
- General well-being assessment

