6.5.3 Adverse Events

Summary Tables

Goal: To present adverse events organized by drug dose, defined here as total amount of study drug per session near AE or reaction, including initial dose and supplement if administered, , seriousness, severity and relatedness to the study drug

Population: All enrolled, Intention to treat, Per protocol, Partial crossover, Extended Assessment 1, Extended Assessment 2

Categorical data includes: Number of AEs per subject; Number of severe AEs; Instances of occurrence of each spontaneously reported reactions by condition (MDMA, Placebo) and Stage (Stage 1, Stage 2); Adverse events (AE identity, seriousness (Yes/No), severity (mild, moderate, severe), onset, resolution, relatedness to study drug (not related, possibly related, probably related); Spontaneously reported reactions listed by MedDRA (Version 14) System Order Class

Format of presentation: This data will be presented in several summary tables of counts per subject, by drug dose, or across the course of the study, as appropriate for the data or descriptive statistics being listed.

Content of Presentation: Number of AEs per subject; Number of severe AEs; Instances of occurrence of each spontaneously reported reactions by condition (MDMA, Placebo) and Stage (Stage 1, Stage 2), number of severe spontaneously reported reactions;Adverse events (AE identity, seriousness (Yes/No), severity (mild, moderate, severe), onset, resolution, outcome, relatedness to study drug (not related, possibly related, probably related); Spontaneously reported reactions listed by MedDRA Version 14 System Order Class

Descriptive data includes: Overall number of AEs, severity of AEs, Peak Demeanor after each experimental and open label session, Overall number of spontaneously reported reactions, average reported severity of spontaneously reported reactions

Format of Presentation: Summary tables of frequency listings in total, by condition, by session, by subject and by condition

Content of Presentation: Adverse Event Listings (All possibly and probably related AEs, all AES occurring within seven days of drug administration, all severe AEs, and number of severe AEs by condition); AE or severity of AE and peak demeanor after each experimental or open label session by condition (MDMA, placebo, partial crossover).

Tabular Listing of Adverse Events

Goal: To follow guidance for display of adverse events

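### SAP 6.5.3 compares adverse-event counts by condition with no common window, exposure denominator or rule for events after crossover, so dose is confounded with observation time

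*SAP*

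**What the plan says.** SAP 5.2 gives spontaneously reported reactions a window (the session and seven days after it). The next item, "Adverse events reported during the study", has none.

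SAP 6.5.3 then plans several kinds of output:

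- Counts with no window: AEs per subject, the overall number of AEs, and "all severe AEs, and number of severe AEs by condition".
- Outputs limited in time: a listing of AEs within seven days of dosing, and AE or severity after each session by condition, with partial crossover as its own group.
- Analysis #1, a formal test. It counts AEs over Stages 1, 2 and 3 and, for Extended Assessment 1 participants, adds AEs up to the 2-, 6- and 12-month visits. Condition (125 mg, 25 mg and, where applicable, 150 mg) is a between-groups factor. There is no exposure term.

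The summary-table goal defines dose as the amount given in the session near the AE, without saying how near. SAP 6.5 lists partial crossover and both extended-assessment groups as separate columns.

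On the schedule, protocol 2.8.2 sets the T5 visit at "12 months after the third experimental session (MDMA 3) for all participants assigned to the Fully Active Dose condition", and also for low-dose participants who decline Stage 2. Protocol 2.8.6 breaks each participant's blind after the T2 measures and offers Stage 2 to the low-dose group: "If the participant consents to take part in Stage 2 of the study, he or she would receive the Fully Active dose".

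**The concern.** A count of AEs grows with the time over which AEs are collected. A low-dose participant who enters Stage 2 has no further time on 25 mg alone after about T2, whereas a full-dose participant can be followed to 12 months after session 3. A by-condition count over unequal times mixes the effect of dose with the length of observation.

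The later time also differs in kind. Under protocol 2.7.1 (items 6 and 7) the limits on psychotropic medication and new psychotherapy end at T3, and after T2 participants know which dose they had.

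Safety is the first study question in both documents. These tables and Analysis #1 are where a reader would look for a dose difference in AEs. With 8 v 4 participants, a few background events in a longer window could change the picture.

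**Working it through.** The documents give no AE rate, expected count or AE window, so there is no figure of the plan to reproduce. The check is person-time arithmetic: at an equal constant rate, the ratio of AEs per subject equals the ratio of the observation windows.

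**Inputs from the documents**

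- Allocation (protocol 2.8.1): "Eight of 12 subjects, or 66.6%, will be assigned to the Fully Active dose condition", so 8 v 4.
- Session interval g (protocol 2.8.4): "the three experimental sessions will be scheduled three to five weeks apart". Protocol 2.8.1 instead has the second and third sessions "scheduled to fall two to four weeks after the previous experimental session". These passages contradict each other and must be reconciled. I use 3 to 5 weeks as the base case and show the effect of 2 to 4.
- T2 is 3 weeks after session 3, T3 is 2 months after it (8.7 weeks) and T5 is 12 months after it (52.2 weeks).
- Stage 2 (protocol 2.8.6): preparation 1 to 2 weeks before its first session, sessions 2 to 4 weeks apart.

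**Assumptions:** equal constant AE rate in both arms; 0 to 4 low-dose participants crossing over; 0 to 100% of AEs tied to sessions; Stage 2 preparation starting at T2.

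**Windows in weeks from first dose:** T2 = 2g + 3; T3 = 2g + 8.7; T5 = 2g + 52.2.

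**Reading A: post-crossover AEs leave the 25 mg column, and all four cross over**

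| g | T2 | T3 | T5 | T3/T2 | T5/T2 |
|---|---|---|---|---|---|
| 3 | 9 | 14.7 | 58.2 | 1.63 | 6.46 |
| 5 | 13 | 18.7 | 62.2 | 1.44 | 4.78 |

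With the 2- to 4-week interval the ratios are 1.81 to 1.52 (T3) and 8.03 to 5.47 (T5). Raw totals double every ratio because of the 8:4 allocation: at 3 to 5 weeks, 3.3 to 2.9 (T3) and 12.9 to 9.6 (T5).

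*Fewer crossing over.* Decliners are followed to T5, so with k of 4 crossing the mean 25 mg window is [k × T2 + (4 − k) × T5]/4. At g = 3, for k = 0, 1, 2, 3, 4, the ratio to 12 months is 1.00, 1.27, 1.73, 2.73, 6.46.

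*Session-linked AEs.* If a share s of the AEs up to T2 is tied to sessions, the ratio is s + (1 − s) × (window ratio). For s = 0.8:

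- To 2 months: 0.8 + 0.2 × 1.63 = 1.13 (g = 3) or 1.09 (g = 5).
- To 12 months: 0.8 + 0.2 × 6.46 = 2.09 (g = 3) or 1.76 (g = 5).

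For s = 1 the ratio is 1.00.

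**Reading B: post-crossover AEs stay with the randomised arm**

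The 25 mg window becomes T2 + preparation + two Stage 2 intervals + follow-up.

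- g = 3, preparation 2, interval 4: 9 + 2 + 8 + 8.7 = 27.7 weeks, and 14.7/27.7 = 0.53. To 12 months, 58.2/71.2 = 0.82.
- g = 5, preparation 1, interval 2: 13 + 1 + 4 + 8.7 = 26.7 weeks, and 18.7/26.7 = 0.70. To 12 months, 62.2/70.2 = 0.89.

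**Common window to T2**

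9 v 9 weeks (g = 3) or 13 v 13 weeks (g = 5): ratio 1.00 under either reading. The seven-day outputs already have this property: 3 × 7 = 21 days in each arm if all three sessions are given.

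**The case against.** A reader might infer that every AE table counts every AE and that full dose must therefore look more harmful, by up to 6.5 times. The documents do not support that.

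- **Not every output is affected.** The seven-day listing and the by-session outputs are limited in time, and SAP 6.5 gives the crossover and extended-assessment groups their own columns. In Analysis #1 follow-up is added only to the overall AE count; the severe-AE count is described by stages alone.
- **The direction is not fixed.** The SAP never assigns post-crossover AEs to the randomised arm, the dose of the nearby session or the crossover group. The separate crossover column, the session-based dose definition and the use of 150 mg (to which nobody was randomised) as a level of condition all favour Reading A, but they are not a rule.
- **The 25 mg window closes at T2 only for those who cross over,** and the documents do not say how many did.
- **The 12-month figure needs every full-dose participant to contribute AEs to T5.** SAP 6.4.2 (Analysis #4) speaks of three participants with 2-, 6- and 12-month assessments. If all three were full dose and the other five stopped at T2, the mean window at g = 3 is (3 × 58.2 + 5 × 9)/8 = 27.45 weeks, a ratio of about 3.05. How actively AEs were sought in late follow-up is not stated.
- **Limiting to Stage 1 might be enough.** The demographic analysis in SAP 6.4.2 treats the end of Stage 1 as three weeks after session 3, which is T2. One cannot say that a Stage 1 limit would leave the imbalance in place.
- **The stated safety hypothesis is the absence of serious AEs at full dose,** not a difference in AE rates. The individual AE listing gives onset, timing after the last dose and stage, so a careful reader of 12 cases could see the unequal windows.

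All of this stands, and it limits the size and removes a claim of direction. It does not rescue the unwindowed by-condition counts or Analysis #1, which pools stages and follow-up and then tests by condition.

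**Conclusion.** The point holds as a non-directional one. Followed as written, Analysis #1 and the unwindowed counts in SAP 6.5.3 compare conditions over observation times that can differ, with no denominator to correct for it.

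At equal constant rates, with sessions 3 to 5 weeks apart and all four low-dose participants crossing over, the ratio of AEs per subject (125 mg to 25 mg) is 1.4 to 1.6 to 2 months on the reading that the SAP's own columns suggest. It is 4.8 to 6.5 to 12 months as an upper case. It shrinks as fewer cross over or as more AEs are session-linked, and reaches 1.0 if none cross or all are. On the opposite attribution it is about 0.5 to 0.9, so full dose would look falsely safer. The AE rate, the number crossing over and the session-linked share are assumptions, because the documents give none of them.

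**What to change.** In SAP 6.5.3, including Analysis #1, restrict every 125 mg v 25 mg comparison of AE and severe-AE counts to events with onset from the first experimental dose to T2 in both arms. Report them per subject, because the allocation is 8:4. Name T2 rather than Stage 1 as the cut-off, since the SAP does not formally define where Stage 1 ends. Apply the same limit to any such contrast taken from Analyses #2 and #3, which also count AEs over all stages.

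Tabulate AEs from Stage 2, Stage 3 and follow-up after T2 separately, by treatment received and with follow-up time, without comparison to 25 mg. The seven-day and by-session outputs can stay as they are.

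The cost is small: a sentence or two in the SAP, using onset dates that it already requires. T2 also precedes the individual unblinding, so the comparison rests on the blinded period. The downside is that late AEs move to a non-comparative table; they are still reported in full.

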Population: All enrolled, intention to treat, per protocol, partial crossover, Extended Assessment 2

Data included: Per each AE; Subject number, Patient identifier

- Age, race, sex, weight (height, if relevant)
- Location of CRFs, if provided
- Adverse event description (preferred term, reported term)
- Duration of the adverse event
- Severity (e.g., mild, moderate, severe)
- Seriousness (serious/non-serious)
- Action taken (none, dose reduced, treatment stopped, specific treatment instituted etc.)
- Outcome (e.g., CIOMS format)
- Relatedness process of determination given if possible
- Date of onset or date of clinic visit at which the event was discovered
- Timing of onset of the adverse event in relation to last dose of investigational product (if or when applicable)
- Investigational product dose in absolute amount, mg/kg
- Duration of investigational product treatment (Stage 1, Stage 2, Stage 3)
- Concomitant treatment during study.

Format of presentation: All adverse events for each patient, including the same event on several occasions will be listed, giving both preferred term and the original term used by the investigator. The listing should be by treatment group and will include:

Analysis #1

Goal: To see if one or more demographic factor and condition alter the number and severity of adverse events and spontaneously reported reactions collected across the course of the study.

Population: All enrolled, intention to treat, per protocol, partial crossover, Extended assessment 1, Extended assessment 2

Data included: Number of AEs collected across Stage 1, Stage 2 and Stage 3, and any AEs collected before 2, 6 and 12 month follow up for Extended Assessment 1 participants, Number of severe AEs collected across Stage 1, Stage 2 and Stage 3 (when applicable), average severity rating of AEs occurring during the study, number of individual spontaneously reported reactions and average severity of self-reported reactions.

Format of analysis: Two-way ANOVA for gender, linear regression analysis for age

Between-groups factors: Condition (125 mg MDMA, 25 mg MDMA, 150 mg MDMA (when applicable)); gender; age

Analysis #2

Goal: to see if there is an effect of presence versus absence of supplemental dose upon number of AEs and spontaneously reported reactions and number of severe AEs and spontaneously reported reactions.

Population: All enrolled, intention to treat, per protocol, partial crossover, extended assessment 2

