Data included: Number of AEs across all study stages, number of severe AEs across all study stages

Format of analysis: One-way ANOVA

Between groups factor: Dosage (25 mg MDMA, 37.5 mg MDMA, 125 mg, 187.5 mg, 150 mg MDMA, 212.5 mg MDMA, 225 mg MDMA)

Analysis #3

Goal: To see if demographic variables interact with dose of study drug; performed if and only if a previous analysis establishes that gender, age or presence of another affective disorder produce an interaction with condition.

Population: All enrolled, intention to treat, per protocol, partial crossover, Extended assessment 1, Extended assessment 2

Data included: Number of AEs across all study stages, number of severe AEs across all study stages.

Format of analysis: Two-way ANOVA for categorical data, regression analysis for continuous data

Between-group factors: Demographic factor (gender (male, female), age, presence of another affective disorder), study drug dose (25 mg, 37.5 mg, 125 mg, 187.5 mg, 150 mg, 212.5 mg, 225 mg MDMA)

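### SAP 6.5.3 Analyses #1 to #3 compare all-stage AE counts between dose groups with no allowance for repeated participants or unequal session numbers

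*SAP*

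**What the plan says.** SAP 6.5.3 (Adverse Events) plans three tests.

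- **Analysis #1** uses, among other outcomes, "Number of AEs collected across Stage 1, Stage 2 and Stage 3, and any AEs collected before 2, 6 and 12 month follow up"; the follow-up part applies to Extended Assessment 1 participants only. The method is two-way ANOVA for gender and linear regression for age. The factors are given as "Between-groups factors: Condition (125 mg MDMA, 25 mg MDMA, 150 mg MDMA (when applicable)); gender; age".
- **Analysis #2** aims "to see if there is an effect of presence versus absence of supplemental dose upon number of AEs and spontaneously reported reactions", plus the severe ones. Its data are "Number of AEs across all study stages, number of severe AEs across all study stages" and its method is one-way ANOVA. The factor is "Between groups factor: Dosage (25 mg MDMA, 37.5 mg MDMA, 125 mg, 187.5 mg, 150 mg MDMA, 212.5 mg MDMA, 225 mg MDMA", seven levels in all.
- **Analysis #3** crosses a demographic factor with the same seven levels. It is "performed if and only if a previous analysis establishes that gender, age or presence of another affective disorder produce an interaction with condition".

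All three list the partial crossover and Extended Assessment 2 populations. None mentions a subject or repeated-measures term, a session count or time at risk.

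The summary-table part of 6.5.3 treats dose per session, "defined here as total amount of study drug per session near AE or reaction", and lists "all AES occurring within seven days of drug administration". That definition is not carried into the three tests, and its closeness criterion has no time window. SAP 6.5.1 handles the same structure for vital signs: Analysis #1 is run separately for each experimental session, and #2 and #3 are repeated-measures analyses over sessions.

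**The concern.** A between-groups ANOVA on counts needs independent groups with comparable exposure. This design gives neither.

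A low-dose participant who enters Stage 2 has sessions at both 25 and 125 mg, and Stage 3 can add sessions at 125 or 150 mg (Protocol 2.5, 2.8.6, 2.8.7). The supplement is decided session by session (Protocol 2.8.1, 2.8.5.1), so one person's sessions can also split between, say, 125 and 187.5 mg. A level with fewer sessions then has a lower count for that reason alone.

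In Analysis #2 the factor also does not match the goal. An overall test of seven total doses mixes differences in initial dose with the effect of the supplement.

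At stake is a reported dose or supplement difference that reflects only session numbers, or a real one that is missed.

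**Working it through.** **Inputs from the documents.** Allocation is 8 full dose to 4 low dose (Protocol 2.8.1). Stage 1 has three sessions, Stage 2 three more at full dose, and Stage 3 two more at 125 or 150 mg (Protocol 2.5, 2.8.6, 2.8.7). Three participants entered Stage 3 (SAP 4.0). The level of 0.05 is from Protocol 2.8.3. The plan gives no error rate or power for the AE tests, so there is no figure to reproduce.

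**Assumed, because the documents do not give them.** Poisson AEs at the same rate per session at every dose; a gamma person effect with coefficient of variation CV; the number crossing over; the frequency of withheld supplements. Follow-up AEs, the gender factor in #1 and the 212.5 mg level are not modelled.

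**Step 1, sessions per person at each level.** 25 mg: 3. 125 mg: 3, or up to 3 + 2 = 5 if Stage 3 uses 125 mg. 150 mg: at most 2, which is 2/3 of the expected count of a three-session level.

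**Step 2, dose received, one row per person per dose.** Rates of 1 or 2 AEs per session; 2 or 4 of the 4 low-dose participants cross over; for #2, the supplement is withheld at random in 10, 20 or 30% of sessions. Approximate false-positive rates:

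| Test | CV 0 | CV 0.4 | CV 0.8 |
|---|---|---|---|
| #1 with a 150 mg level | 8-15% | about 5% | 1-2% |
| #2 Dosage factor | 8-36% | 5-16% | 1-4% |

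For #1 with Stage 3 given at 125 mg, the 25 v 125 mg contrast gives about 0.6-4.9% over all settings. Unequal sessions push the rate up. Treating one person's rows as independent pushes it down once people differ.

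**Step 3, why #2 moves most.** Let q be the chance that the supplement is withheld. Among participants with three full-dose sessions who contribute to a level, mean sessions are 3q/(1-(1-q)^3) not given and 3(1-q)/(1-q^3) given. For q = 0.1, 0.2, 0.3 these are 1.11, 1.23, 1.37 and 2.70, 2.42, 2.16, so the ratios are 41, 51 and 63%. They compare different sets of contributors. For one participant whose three sessions do split, the means are 1+q and 2-q, so the ratios are 1.1/1.9, 1.2/1.8 and 1.3/1.7, or 58, 67 and 76%.

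**Step 4, assigned arm, all-stage totals per person.** Rates of 1 to 3 AEs per session and CV 0 to 1.0.

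- All four cross over, no Stage 3: 0.18-0.96.
- All four cross over, three Stage 3 participants from the full-dose arm: 0.11-0.61.
- All four cross over, Stage 3 with one full-dose and two low-dose participants: 0.20-0.97.
- Two or none cross over, three Stage 3 participants from the full-dose arm: about 0.03-0.06.

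Direction, with 1 AE per low-dose and 2 per full-dose session: the low-dose total is 3×1 + 3×2 = 9. The full-dose total is 3×2 = 6, or 6 + 2×2×3/8 = 7.5 with three of eight in Stage 3. The sign is reversed. With no crossover it would be 3.0 v 7.5.

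**Step 5, one row per session, no subject term** (25/125/150 mg factor). Exposure is equal, but rows from one person are correlated: 0.05 at CV 0, 0.06-0.13 at CV 0.5, 0.07-0.21 at CV 1.0.

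**Step 6, one row per person with seven dose levels.** 12 - 7 = 5 error degrees of freedom, and a person treated at several doses has no single level.

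**The case against.** The best defence has four parts.

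- **Little inflation in #1.** Under dose received, 25 v 125 mg is not inflated. The 150 mg level matters only if people have nearly identical rates, and only if someone received that dose. The factor says when applicable, and the documents do not say that anyone did. This stands.
- **The size in #2 is assumed.** No document gives a frequency for withheld supplements. This stands; the ranges are illustrations. A reader might also infer that unsupplemented sessions will look worse because the supplement may be withheld for warning signs. That holds only if such signs are recorded as AEs, and its size cannot be derived.
- **Later stages may be kept apart.** SAP 6.5 tabulates partial crossover and the extended assessments as separate conditions. This is fair for the tables. The test factors, however, name only doses while the outcomes sum all stages.
- **Little depends on these tests.** The safety hypothesis (Protocol 2.6) concerns serious events and tolerability, 6.5.3 already lists each event with dose, stage and timing, and #3 is conditional. This stands and sets the severity.

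The defence does not supply the missing subject term or denominator, and no choice of row removes the need for both.

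**Conclusion.** The point holds as a minor flaw, with moderate confidence. The stated tests ignore repeated participants and unequal sessions under every available reading. Their error can go either way, depending on between-person spread, the withholding frequency, the number crossing over and the definition of Condition and row.

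Dose received is the more natural reading, given the 150 mg level, the crossover population and the same factor in SAP 6.5.1. It is not certain, and the assigned-arm reading gives the largest errors.

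Three stronger inferences are not supported.

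- **That the tests generally produce false dose effects.** At CV 0.8 they are conservative, and 25 v 125 mg by dose received does not exceed the nominal level.
- **That a dose effect will be reversed.** This needs the assigned-arm reading and substantial crossover, and the documents do not give the number crossing over.
- **That the trial's safety conclusion is compromised.** The SAE question is answered by counts and listings, and the average-severity outcomes in #1 are not inflated by extra sessions.

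The follow-up AEs added for one subset are a further imbalance that has not been sized.

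**What to change.** - **Condition comparison in #1:** test Stage 1 AEs only, from first dose to T2, by randomised arm. Planned exposure is then three sessions for everyone, and the simulated false-positive rate is 3.9-5.1%.
- **Later stages, and the dose factor in #2 and #3:** use AEs per session by dose received, with the summary-table dose definition and a stated window. The seven days already used for a listing would serve. Report descriptively or, if tested, at session level with a subject term (simulated 3.3-6.4% for #1 and 3.7-7.6% for #2). Dividing by sessions without a subject term is not enough: #2 then gives 2.9-13.7%.
- **Supplement given v not given:** report descriptively per session.
- **Gender and age questions:** keep them, on the same per-session outcome.
- **Follow-up AEs:** keep them in listings.

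The cost is SAP wording and re-tabulation of data that 6.5.3 already lists per event; no new data are needed. Later-stage AEs lose most formal testing, and events outside the window appear only in listings. Stage 1 power for a doubled AE rate is low and uncertain: about 8% to 82% over the assumed rates and spreads, and about 27-37% at CV 0.4. A non-significant result there should not be read as absence of a dose effect.
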